PCI Status	1=elective; 2=urgent; 3=emergency; 4=salvage	
 
1. Elective: The procedure can be performed on an outpatient basis or during a subsequent hospitalization without significant risk of infarction or death. For stable inpatients, the procedure is being performed during this hospitalization for convenience and ease of scheduling and NOT because the patient's clinical situation demands the procedure prior to discharge. If the diagnostic catheterization was elective and there were no complications, the PCI would also be elective. 
2. Urgent: The procedure should be performed on an inpatient basis and prior to discharge because of significant concerns that there is risk of ischemia, infarction and/or death. Patients who are outpatients or in the emergency department at the time that the cardiac catheterization is requested would warrant an admission based on their clinical presentation. 
3. Emergency: The procedure should be performed as soon as possible because of substantial concerns that ongoing ischemia and/or infarction could lead to death. "As soon as possible" refers to a patient who is of sufficient acuity that you would cancel a scheduled case to perform this procedure immediately in the next available room during business hours, or you would activate the on-call team were this to occur during off-hours. 
4. Salvage: The procedure is a last resort. The patient is in cardiogenic shock when the PCI begins (i.e. at the time of introduction into a coronary artery or bypass graft of the first guidewire or intracoronary device for the purpose of mechanical revascularization). Within the last ten minutes prior to the start of the case or during the diagnostic portion of the case, the patient has also received chest compressions for a total of at least

Data Field Term	VALUE	Description/Definition
		
sixty seconds or has been on unanticipated extracorporeal circulatory support (for example, extracorporeal mechanical oxygenation, or cardiopulmonary support).
 
Code the best estimate of current left ventricular ejection fraction. Target Value: The last value between 6 months prior to current procedure and prior to the intervention

PCI Indication	
1=Immediate PCI for STEMI; 2= PCI for STEMI, unstable > 12 hours; 3=PCI for STEMI, stable > 12 hours; 4=PCI for STEMI stable after successful lytics; 5=Rescue PCI for STEMI after failed lytics; 6=PCI for high risk NSTEMI or unstable angina; 7= Staged PCI; 8=Other
	
Selection Text Definition
 
 1. Immediate PCI for STEMI: Immediate PCI for patient with STEMI (or STEMI equivalent). 2. PCI for STEMI (Unstable, >12hrs from Sx onset): PCI for STEMI (or STEMI equivalent) more than 12 hours from symptom onset with recurrent or persistent symptoms, symptoms of heart failure or ventricular arrhythmia. 3. PCI for STEMI (Stable, >12 hrs from Sx onset): Patient with STEMI (or STEMI equivalent) who is stable, and is more than 12 hours from symptom onset. The patient does not have any symptoms of recurrent or persistent ischemia, symptoms of heart failure, or electrical instability. 4. PCI for STEMI (Stable after successful full-dose Thrombolysis): PCI for STEMI (or STEMI equivalent) who is stable after receiving full dose thrombolysis. 5. Rescue PCI for STEMI (after failed full-dose lytics): Rescue PCI for STEMI (or STEMI

Data Field Term	VALUE	Description/Definition
		
equivalent) after failed full-dose lytics.
 
6. PCI for high risk Non-STEMI or unstable angina: Includes patients with unstable angina or Non-STEMI who have high risk features for short-term risk of death or nonfatal MI. High risk features includes at least one of the following:
 
 a. History - accelerating tempo of ischemic symptoms in preceding 48 hours. b. Character of pain - prolonged ongoing (greater than 20 minutes) rest pain. c. Clinical findings: 
 i. Pulmonary edema, most likely due to ischemia ii. New or worsening mitral regurgitation murmur iii. S3 or new worsening rales d) Hypotension, bradycardia, tachycardia iv. Age greater than 75 years v. ECG vi. a) Angina at rest with transient ST-segment changes greater than 0.5 mm vii. Bundle-branch block, new or presumed new viii. Sustained ventricular tachycardia ix. Cardiac markers - NSTEMI patients with elevated cardiac TnT, Tnl, or CK-MB. x. Staged PCI The second PCI of a planned, staged procedure (the first PCI could have been during a prior admission, or during this admission). xi. Other: Includes patients that don't fit into any of the above categories. This can include patients with elective or urgent status, status/post

Data Field Term	VALUE	Description/Definition
		cardiac arrest or cardiogenic shock but without ECG or biomarker evidence of acute infarction.
Stress or Imaging pre procedure	0=no, 1=yes	For any subsequent procedures during this episode of care, only code new imaging or stress test results that were performed after the previous procedure until the current procedure.
Beta Blocker on admit	0=no, 1=yes	Indicate if the patient has taken or has been prescribed a beta blocker to treat anginal symptoms. Target Value: Any occurrence between 2 weeks prior to current procedure and current procedure Note(s): Code 'no' if a patient was given a sublingual, IV, or short acting formula of one of these medications. Code 'yes' if the patient was started on an oral form of a beta-blocker after admission but prior to this cath lab visit. If this medication was prescribed for this patient, but you are unsure if it has been prescribed specifically to treat anginal symptoms, code 'yes'.
Ca channel blocker on admit	0=no, 1=yes	Indicate if the patient has taken or has been prescribed a calcium channel blocker to treat anginal symptoms. Target Value: Any occurrence between 2 weeks prior to current procedure and current procedure Note(s): Code 'no' if a patient was given a sublingual, IV, or short acting formula of one of these medications. Code 'yes' if the patient was started on an oral form of a calcium channel blocker after admission but prior to this cath lab visit. If this medication was prescribed for this patient, but you are unsure if it has been prescribed specifically to treat anginal symptoms, code 'yes'.
ASA on admission	0=no, 1=yes	Indicate if the patient is currently taking aspirin at the time of admission.

Data Field Term	VALUE	Description/Definition
Clopidogrel on admission	0=no, 1=yes	Indicate if the patient is currently taking clopidogrel at the time of admission.
Prasugrel on admission	0=no, 1=yes	Indicate if the patient is currently taking prasugrel at the time of admission.
Ticagrelor on admission	0=no, 1=yes	Indicate if the patient is currently taking ticagrelor at the time of admission.
Nitrate on admit	0=no, 1=yes	Indicate if the patient is currently taking nitrates at the time of admission.
Ranexa on admit	0=no, 1=yes	Indicate if the patient has taken or has been prescribed Ranolazine to treat anginal symptoms. Target Value: Any occurrence between 2 weeks prior to current procedure and current procedure Note(s): Code 'no' if a patient was given a sublingual, IV, or short acting formula of one of these medications. Code 'yes' if the patient was started on an oral form of Ranolazine after admission but prior to this cath lab visit. If this medication was prescribed for this patient, but you are unsure if it has been prescribed specifically to treat anginal symptoms, code 'yes'.
Procedural ASA	0=no, 1=yes	Indicate if the patient was administered aspirin at any time during index procedure
Procedural Fondaparinux	0=no, 1=yes	Indicate if the patient was administered fondaparinux at any time during index procedure
Procedural LMWH	0=no, 1=yes	Indicate if the patient was administered a low-molecular heparin at any time during index procedure
Procedural UFH	0=no, 1=yes	Indicate if the patient was administered fondaparinux at any time during index procedure
Procedural Bival	0=no, 1=yes	Indicate if the patient was administered bivalirudin at any time during index procedure
Procedural IIb/IIIa	0=no, 1=yes	Indicate if the patient was administered IIb/IIIa inhibitor at any time during index procedure
Clopidogrel loading	0=no, 1=yes	Indicate if the patient was administered a loading

Data Field Term	VALUE	Description/Definition
		dose of clopidogrel
Prasugrel loading	0=no, 1=yes	Indicate if the patient was administered a loading dose of prasugrel
Ticagrelor loading	0=no, 1=yes	Indicate if the patient was administered a loading dose of ticagrelor
Discharge ACE-I or ARB	0=no, 1=yes	At the time of discharge, was the patient prescribed an ACE-Inhibitor (or ARB)
Discharge ASA	0=no, 1=yes	At the time of discharge, was the patient prescribed aspirin
Discharge bbl	0=no, 1=yes	At the time of discharge, was the patient prescribed a beta blocker
Discharge Statin	0=no, 1=yes	At the time of discharge, was the patient prescribed a statin
Discharge Clopidogrel	0=no, 1=yes	At the time of discharge, was the patient prescribed clopidogrel
Discharge Clopidogrel 75 mg	0=no, 1=yes	At the time of discharge, was the patient prescribed clopidogrel 75mg
Discharge Clopidogrel 150 mg	0=no, 1=yes	At the time of discharge, was the patient prescribed clopidogrel 150mg
Discharge Prasugrel	0=no, 1=yes	At the time of discharge, was the patient prescribed prasugrel
Discharge Prasugrel 5mg	0=no, 1=yes	At the time of discharge, was the patient prescribed prasugrel 5mg
Discharge Prasugrel 10mg	0=no, 1=yes	At the time of discharge, was the patient prescribed prasugrel 10mg
Discharge Ticagrelor	0=no, 1=yes	At the time of discharge, was the patient prescribed ticagrelor
Discharge Anticoagulant	0=no, 1=yes	At the time of discharge, was the patient prescribed an anticoagulant (warfarin; LMWH; rivoraxaban)
Multivessel disease	0=no, 1=yes	Value is 1 if number of diseased vessels > 1
Number of lesions treated	##	Total number of lesions treated during the index PCI

Data Field Term	VALUE	Description/Definition
Number of stents implanted	##	Total number of stents implanted during index PCI
mean stent diameter	### mm	Mean diameter of all stents implanted during index PCI
Total stent length	## mm	Total length of all stents implanted during index PCI
At least 1 type B2/C lesion	0=no, 1=yes	Does patient have at least 1 type B2/C Lesion
At least 1 lesion with moderate/severe calcifications	0=no, 1=yes	Does patient have 1 lesion with moderate/severe calcifications
At least 1 bifurcation lesion	0=no, 1=yes	Does patient have at least 1 bifurcation lesion
At least one bare metal stent	0=no, 1=yes	yes if any BMS used to treat any lesion during index PCI
At least one drug eluting stent (1st gen)	0=no, 1=yes	yes if any 1st generation DES used to treat any lesion during index PCI
At least one drug eluting stent (2nd gen)	0=no, 1=yes	yes if any 2nd generation DES used to treat any lesion during index PCI
PCI vessel LM	0=no, 1=yes	PCI was performed of LM
PCI vessel LAD	0=no, 1=yes	PCI was performed of LAD
PCI vessel LCx	0=no, 1=yes	PCI was performed of LCx
PCI vessel RCA	0=no, 1=yes	PCI was performed of RCA
Post procedure MI	0=no, 1=yes	Indicate the NEW occurrence of a biomarker positive myocardial infarction after PCI. At least one determination of biomarkers obtained no sooner than 6 hours after PCI, and preferably within the interval of 6-24 hours post-PCI, should be used to make this diagnosis. Target Value: Any occurrence between start of procedure and until the next procedure or until discharge. Note(s): Q waves with absent, incomplete or inconclusive biomarkers should be considered evidence of MI and should be

Data Field Term	VALUE	Description/Definition
		
coded as yes. In rare situations, biomarkers may not be obtained in the setting of a post-PCI acute MI (for example, sudden unexpected cardiac death without symptoms or ECG changes suggestive of ischemia, patient is transferred, or biomarkers were just not ordered). In these situations, the site may choose to report a clinically-diagnosed post-PCI myocardial infarction even in the absence of the usually required biomarker elevations. For patients with extended hospital stays, restrict coding of post-procedure events to 30 days after the last procedure.

Post Procedure Cardiogenic Shock	0=no, 1=yes	
Indicate if the patient had a new onset or acute recurrence of Coding Instructions: cardiogenic shock. Target Value: Any occurrence between start of procedure and until next procedure or discharge. Note(s): Transient episodes of hypotension reversed with IV fluid or atropine do not constitute cardiogenic shock. The hemodynamic compromise (with or without extraordinary supportive therapy) must persist for at least 30 minutes. For patients with extended hospital stays, restrict coding of post-procedure events to 30 days after the last procedure. Cardiogenic shock is defined as a sustained (>30 minutes) episode of systolic blood pressure <90 mm Hg, and/or cardiac index <2.2 L/min/m² determined to be secondary to cardiac dysfunction, and/or the requirement for parenteral inotropic or vasopressor agents or mechanical support (for example, IABP, extracorporeal circulation, ventricular assist devices) to maintain blood pressure and cardiac index above those specified levels.

Data Field Term	VALUE	Description/Definition
Post Procedure Heart Failure	0=no, 1=yes	Indicate if the patient had new onset or acute recurrence of heart failure which necessitated new or increased pharmacologic therapy. Target Value: Any occurrence between start of procedure and until next procedure or discharge Note(s): For patients with extended hospital stays, restrict coding of post-procedure events to 30 days after the last procedure. Heart Failure: A previous hospital admission with a principal diagnosis of heart failure is considered evidence of heart failure history. Heart failure is defined as physician documentation or report of any of the following clinical symptoms of heart failure: unusual dyspnea on light exertion; recurrent dyspnea occurring in the supine position; fluid retention; the description of rales, jugular venous distension, pulmonary edema on physical exam; or pulmonary edema on chest x-ray. A previous hospital admission with principal diagnosis of heart failure is considered evidence of heart failure history. A low ejection fraction without clinical evidence of heart failure does not qualify as heart failure.
Post Procedure CVA/Stroke	0=no, 1=yes	Indicate if the patient had a cerebrovascular Coding Instructions: accident (CVA). Target Value: Any occurrence between start of procedure and until next procedure or discharge Note(s): A stroke or CVA is documented by a loss of neurological function caused by an ischemic or hemorrhagic event with residual symptoms lasting at least 24 hours after onset or leading to death. For patients with extended hospital stays, restrict coding of post-procedure events to 30 days after the last procedure.
Post Procedure Tamponade	0=no, 1=yes	Indicate if the patient experienced fluid in the pericardial space compromising cardiac filling and requiring intervention. Target Value: Any occurrence between start of procedure and until next procedure or discharge Note(s): For patients with extended hospital stays, restrict coding of post-procedure events to 30 days

Data Field Term	VALUE	Description/Definition
		
after the last procedure. Tamponade should be documented by either:
 
 A. Echocardiogram showing pericardial fluid and signs of tamponade such as right heart compromise, or B. Systemic Hypotension due to pericardial fluid compromising cardiac function.
Post Procedure Dialysis	0=no, 1=yes	
Indicate if the patient experienced acute or worsening renal failure necessitating Coding Instructions: renal dialysis. Target Value: Any occurrence between start of procedure and until next procedure or discharge Note(s): If a patient is on receiving continuous veno-venous hemofiltration (CVVH) as a result of renal failure (and not as treatment to remove fluid for heart failure), code yes. For patients with extended hospital stays, restrict coding of post-procedure events to 30 days after the last procedure.

Post Procedure Vascular Complication	0=no, 1=yes	
Indicate if the patient experienced any other vascular complications (excluding external bleeding or hematomas) at the percutaneous entry site that required treatment or intervention. Note: Code 'yes' for patients treated with IV therapy for loss of distal pulse. For patients with extended hospital stays, restrict coding of post-procedure events to 30 days after the last procedure. Target Value: Any occurrence between start of procedure and until next procedure or discharge. Vascular complications can include, but are not limited to, access site occlusions, peripheral embolizations, dissections, pseudoaneurysms and/or AV fistulas. Any noted vascular complication must have had an intervention such as a fibrin injection, angioplasty, or surgical repair to qualify. Prolonged pressure does not qualify as an intervention, but ultrasonic guided compression after making a diagnosis of pseudoaneurysm does qualify. A retroperitoneal bleed or hematoma requiring transfusion is not a vascular complication under this data element. To qualify, this adverse outcome should be attributable

Data Field Term	VALUE	Description/Definition
		to this procedure and not related to a previous or subsequent procedure.
Post Procedure Blood Transfusion	0=no, 1=yes	Indicate if there was a transfusion(s) of either whole blood or packed red blood cells. For patients with extended hospital stays, restrict coding of post-procedure events to 30 days after the last procedure. Target Value: Any occurrence between start of procedure and until next procedure or discharge.
Units of Blood Transfused	##	Number of prbc transfused. Leave as missing if pp_trans = 0.
Post Procedure Bleeding event (72 hours)	0=no, 1=yes	Note(s): A patient who was actively bleeding with coffee ground emesis pre-procedure should not qualify as bleeding. However, a patient with peptic ulcer disease with no noted or active bleeding prior to procedure who starts bleeding after the procedure would qualify as a "yes".
Death (all)	0=no, 1=yes	Report of patient death
Death (all) date	DDMMYYYY	Date of death
Type of Death	1=cardiac, 2=noncardiac, 3= unknown	Enter type of death
Myocardial infarction	0=no, 1=yes	hospitalization for acute (spontaneous) MI after index PCI
Myocardial infarction date	DDMMYYYY	date of event
Number of acute MI hospitalization until		Total number of acute MI hospitalization from 1/1/2010 - 12/31/2012

Data Field Term	VALUE	Description/Definition
12/31/2012		
Unplanned revascularization	0=no, 1=yes	Hospitalization for unplanned revascularization with CABG or PCI after index PCI
Unplanned revascularization date	DDMMYYYY	date of event
Number of unplanned revascularization hospitalization until 12/31/2012		Total number of unplanned revascularization hospitalization from 1/1/2010 - 12/31/2012
Bleeding	0=no, 1=yes	Hospitalization for bleeding after index PCI
Bleeding date	DDMMYYYY	date of event
Number of bleeding hospitalization until 12/31/2012		Total number of bleeding hospitalizations from 1/1/2010 - 12/31/2012
Type of Bleeding	1=access site; 2=GI; 3=GU; 4=CNS; 5=other; 6=unknown	1)access site 2) GI 3) GU 4) CNS 5) Other 6) Unknown
Stroke	0=no, 1=yes	Was the patient diagnosed as having a stroke
Stroke date	DDMMYYYY	Date of event
Stroke type	1=ischemic; 2=hemorrhagic; 3= unknown	1) Ischemic 2) hemorrhagic
Number of stroke hospitalizations until 12/31/2012		Total number of stroke hospitalizations from 1/1/2010 - 12/31/2012
Definite/Prob ST	0=no, 1=yes	Hospitalizations for Definite/Probable Stent Thrombosis
Definite/Prob ST date	DDMMYYYY	Date of Event

Data Field Term	VALUE	Description/Definition
last follow up date	DDMMYYYY	Last date of encounter with patient

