3.3.3. Study Populations

Inclusion criteria: Adult patients:

1. At least 18 years of age
2. Diagnosed with ACS (STEMI, NSTEMI, UA) and managed by PCI during index hospitalization between 01 January 2010 and 30 June 2013
3. Initiated use of prasugrel or clopidogrel during index hospitalization either prior to, during, or in the peri-procedural period (as defined below) of the index PCI and were discharged on the same medication as initiated during the peri-procedural period. Patients initiated on 1 agent prior to PCI and then switched to the other agent in the peri-procedural period (prior to, during, or ≤ 3 hours post-procedure) will also be eligible for analysis.

Subgroups of interest:

1. ACS-PCI patients with no prior TIA or stroke
2. ACS-PCI patients with no prior history of TIA or stroke and are:
 - a. <75 years of age, or
 - b. If ≥ 75 years of age, have diabetes mellitus or a prior history of MI
3. Age ≥ 75 years
4. Diabetes mellitus

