3.4.2. Economic Outcomes Analyses

3.4.2.1. Unadjusted Outcomes Analyses

Data will be gathered on all patients in the study concerning their index and follow-up hospitalizations for MI, stroke, repeat unplanned coronary revascularization and stent thrombosis. The frequency of PCI and/or coronary artery bypass graft (CABG) procedures during these hospitalizations will be captured. The proportion of patients with follow-up hospitalization for these diagnoses will be compared between prasugrel and clopidogrel groups using Chi-square tests. The crude unadjusted rates will be calculated for each group using the Kaplan-Meier method and compared using the log-rank test.

All hospitalizations (except for bleeding-related hospitalizations) will be assigned a DRG based on the diagnoses of interest without knowledge of the patient's treatment assignment. The DRGs will be converted to direct medical costs for hospitalization based on Medicare Part A reimbursement. Bleeding-related rehospitalization costs will not be included in this specific analysis as the specific DRG related to this type of admission cannot be determined in this dataset. An additional cost for physicians will be estimated using the Resource-Based Relative

Value Scale (RBRVS) and the Medicare payment schedule. When a hospitalization includes more than 1 event, the highest paying DRG will be used.

Total direct medical costs for the index hospitalization and subsequent hospitalizations will be totaled. Indirect costs (lost productivity) due to premature CV death will be calculated. Hospital length of stay will be calculated as the number of days from hospital admission to discharge. The difference in mean costs (direct and indirect), length of stay, and other continuous resource utilization outcomes (for example, counts of CV-related hospitalizations per patient) between treatment groups will be calculated using t-tests. Exact tests, bootstrapping and/or nonparametric tests will be used as appropriate.

In Study B020, clinical outcomes are measured by days from index hospital admission whereas health economic outcomes are measured by days from index hospital discharge.

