3.4.8. Sample Size and Power Considerations

Study B020 is designed to assess the difference in MACE associated with prasugrel versus clopidogrel in patients presenting with ACS managed with a PCI from academic centers in the US from 01 January 2010 to 30 June 2013. Data from the Premier study and from TRANSLATE-ACS have suggested that the MACE rate at 90 days will be approximately 8.0%. Using 8.0% as the control rate, it is expected that the relative reduction with prasugrel will be

20% lower than with clopidogrel (hazard ratio 0.80). To achieve 80% power with an alpha of 0.05, and factoring in a 10% patient drop-out, at least 4,303 patients on prasugrel and clopidogrel need to be enrolled, yielding a minimum enrollment of 8,606 patients. If it is necessary to extend the window of time beyond 30 June 2013 in order to enroll an adequate number of patients, no protocol amendment will be required.

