Number of acute MI hospitalization within one year of procedure	##	Total number of acute MI hospitalization within one year of index procedure date

Unplanned revascularization within one year of procedure	0=no, 1=yes	Hospitalization for unplanned revascularization with CABG or PCI within one year of index procedure date
Unplanned revascularization date	DDMMYYYY	Date of event
Number of unplanned revascularization hospitalization within one year of procedure	##	Total number of unplanned revascularization hospitalization within one year of index procedure date
Bleeding within one year of procedure	0=no, 1=yes	Hospitalization for bleeding within one year of index procedure date
Bleeding date	DDMMYYYY	Date of event
Number of bleeding hospitalization within one year of procedure	##	Total number of bleeding hospitalizations within one year of index procedure date.
Type of Bleeding	1=access site; 2=GI; 3=GU; 4=CNS; 5=other; 6=unknown	1)Access site 2) GI 3) GU 4) CNS 5) Other 6)Unknown
Stroke within one year of procedure	0=no, 1=yes	Was the patient diagnosed as having a stroke within one year of index procedure date
Stroke date	DDMMYYYY	Date of event
Stroke type	1=ischemic; 2=hemorrhagic; 3=unknown	1) Ischemic 2) Hemorrhagic
Number of stroke hospitalizations within one year of procedure	##	Total number of stroke hospitalizations within one year of index procedure date.
Definite/Probable ST	0=no, 1=yes	Hospitalizations for Definite/Probable Stent Thrombosis
Definite/Probable ST date	DDMMYYYY	Date of Event

last follow up date	DDMMYYYY	Last date of encounter with patient
---------------------	----------	-------------------------------------

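### The protocol counts hospitalizations over fixed calendar dates ending 31 December 2012 while index PCIs run to 30 June 2013, so per-patient counts are not comparable across entry dates, and the SAP defines the same fields differently.

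*Protocol*

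**What the plan says.** Protocol Attachment 1 has four count fields with the same calendar limits:

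- MI: "Total number of acute MI hospitalization from 1/1/2010 - 12/31/2012"
- Unplanned revascularization: "Total number of unplanned revascularization hospitalization from 1/1/2010 - 12/31/2012"
- Bleeding: "Total number of bleeding hospitalizations from 1/1/2010 - 12/31/2012"
- Stroke: "Total number of stroke hospitalizations from 1/1/2010 - 12/31/2012"

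Protocol 3.3.3 takes patients "managed by PCI during index hospitalization between 01 January 2010 and 30 June 2013". Protocol 3.4.8 allows later entry without an amendment: "If it is necessary to extend the window of time beyond 30 June 2013". Protocol 3.4.1 follows each patient until death, last follow-up or 365 days from admission, whichever is first.

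Protocol 3.4.2.1 gives "counts of CV-related hospitalizations per patient" as an example of a continuous resource-use outcome to be compared between arms by t-tests, with exact, bootstrap or nonparametric methods as appropriate. It mentions no allowance for differing observed time.

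SAP Section 13 (Attachment 1) defines the same four fields per patient. For bleeding it reads "Total number of bleeding hospitalizations within one year of index procedure date". The MI, revascularization and stroke counts use the same one-year window, with no calendar date.

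**The concern.** A count is comparable between patients only if each is observed for the same length of time or the difference is allowed for. With fixed calendar limits, a patient treated in January 2010 is counted for almost three years and one treated in 2013 for no time after the index PCI. The window also opens on 1 January 2010 for everyone. The count definitions, unlike the MI, revascularization and bleeding yes/no fields beside them, do not say that the admission must follow the index PCI. Earlier admissions, and the index MI admission itself, could therefore be counted.

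At stake is the between-arm comparison of hospitalizations per patient. If the mix of prasugrel and clopidogrel changed over the accrual period, the arms would have different average windows and their counts could differ with no drug effect. Protocol 3.4.2.2 adjusts for baseline demographic and clinical characteristics and baseline treatment use. Entry date is not named among the covariates, so that adjustment would not clearly remove the artefact.

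There is also a plain conflict: both attachments define the extracted data, and they give different windows for the same fields.

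**Working it through.** The plan states no figure for lost or gained counting time, so there is none to reproduce. The check is a day count.

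**Inputs from the documents.** Entry runs from 1 Jan 2010 to 30 June 2013 (Protocol 3.3.3): 365 + 365 + 366 + 181 = 1,277 entry days. Counting ends on 31 Dec 2012 (Protocol Attachment 1). The follow-up horizon is 365 days (Protocol 3.4.1).

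**Assumptions not in the documents.** Entry is uniform, there is no death or loss to follow-up, and time runs from the index PCI.

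**Countable time.** For entry date t, days counted after the index = max(0, 31 Dec 2012 − t).

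1. *No countable time:* entry from 31 Dec 2012 to 30 June 2013 = 182 days. 182 / 1,277 = 14.3%.
2. *Some of the first year lost:* entry from 2 Jan 2012 onward = 365 + 181 = 546 days. 546 / 1,277 = 42.8%.
3. *First-year time excluded:* the 364 partly covered entry days lose 1, 2, …, 364 days, a total of 364 × 365 / 2 = 66,430. The 182 uncovered entry days lose 182 × 365 = 66,430. The sum is 132,860, out of 1,277 × 365 = 466,105. Share = **28.5%**.
4. *Time counted beyond day 365:* entry from 1 Jan 2010 to 1 Jan 2012 gains 730, 729, …, 0 days, a total of 730 × 731 / 2 = 266,815. Relative to 466,105 this is **57%**.
5. *Mean counted window:* (466,105 − 132,860 + 266,815) / 1,277 = 600,060 / 1,277 = 470 days, about 15.4 months.

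**Sensitivity to accrual.** Repeating step 3 with entry weights that are linear over the period:

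| Entry rate relative to average | First-year time excluded |
|---|---|
| falls from 1.5 to 0.5 | 18.7% |
| uniform | 28.5% |
| rises from 0.5 to 1.5 | 38.4% |

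The extremes (falling to zero, rising from zero) give 8.8% and 48.2%. These are shares of time, not of events. If events cluster early, with cumulative hazard proportional to the square root of time, the share of first-year events excluded under uniform entry is 23.7%.

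**With the SAP window.** One year from each patient's own index procedure has no calendar cut-off, so the excluded share in step 3 falls to 0% and the gain in step 4 disappears.

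**The case against.** The strongest reply is that the SAP has already dealt with this. It describes the TRANSLATE-ACS registry as completed, cites 2014 results and names eight centers, so it reads as the later document. Its attachment uses a per-patient year, and SAP 7.1 promises sites detailed extraction instructions. If sites work from the SAP sheet, the calendar truncation does not arise. This stands as far as it goes. However, Protocol 3.3.4 still points to Attachment 1 for the dataset's definitions. The SAP text does not say which attachment governs extraction, and it defers the economic methods to Addendum 1.

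The reply also says that these fields are little used. That is fair: the counts appear as a parenthetical example, they are not among the economic objectives listed in Protocol 3.2.2, and SAP mock Table 6 has no row for them.

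A reader might infer more than the documents support:

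- *That events after 2012 are lost to the study.* They are not. Each event type has its own yes/no and date fields with no calendar end. Primary MACE, the Kaplan-Meier and Cox analyses and the readmission proportions need only those.
- *That counts are understated by 29%.* Step 3 shows only the loss. Steps 4 and 5 show a larger gain for early entrants, and admissions before or at the index event could add more. Understatement is not shown.
- *That costs are understated too.* Protocol 3.4.2.1 and SAP 7.1 assign a DRG to each hospitalization. Nothing says that costs are computed from these count fields, and the protocol leaves bleeding admissions out of costs.
- *That one arm would show a 24% lower count.* This figure needs opposite 50% accrual slopes in the two arms (coverage 62% v 81%, with 62 / 81 = 0.76). It also needs a 365-day cap that the protocol field lacks. The documents give no accrual pattern by arm.
- *That the economic methods exist only in the protocol.* SAP 7.1 and the table listing in SAP Section 12 give some of them.

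**Conclusion.** The inconsistency is real and limited in reach. As the protocol words them, the four counts cover a window that depends on entry date, from 1,095 days after the index PCI for the first entrant to none for those entering in 2013. Under uniform entry, 14.3% of patients have no countable post-index time and 28.5% of first-year risk time is excluded (about 19% to 38% for linear slopes of 50% either way). At the same time, early entrants add time beyond day 365 equal to 57% of the first-year total. Entry after June 2013 would add more patients with no countable time.

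The counts are therefore not comparable across entry dates. They could be biased between arms if entry dates differ by arm, in a direction that cannot be determined from the documents. Only the per-patient hospitalization counts are affected. The percentages rest on uniform or linear entry without death or loss to follow-up; that the window varies with entry date needs no such assumption.

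**What to change.** 1. In Protocol Attachment 1, replace the calendar-date wording of the four count fields by the SAP's per-patient one-year window, restricted to admissions after the index hospitalization. The SAP fields need the same restriction, since they do not exclude the index stay.
2. State that this definition governs site extraction and Addendum 1.
3. Settle the starting point. The SAP fields run from the index procedure, whereas Protocol 3.2.2 and 3.4.2.1 measure economic outcomes from index discharge. One clock should be chosen for these counts.
4. Account for observed follow-up when counts are compared. Either use events per unit of person-time, which can keep the planned IPW bootstrap, or use a count model with log observed time as offset. The last follow-up date and date of death needed for this are already in both attachments.

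The cost is minor wording and a small change to the analysis. The fix does not need dates of repeat admissions. Those are on neither sheet (each event type has one date) and would be extra extraction, needed only if counts were wanted for windows shorter than a year.
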